## 3.5 Laboratory testing:

The valve has undergone laboratory testing at the Bristol Urological Institute which show that a simple valve allowing the bladder to naturally 'fill and flush' stops bacteria for more than fourteen days. Glass bladder models were used to evaluate the performance of the valve in situ to demonstrate functionality when compared with free drainage as follows:

1. Catheters were inserted into glass bladder models and set up with the valve housing inserted between the catheter and drainage bag in both models. One model had no valve (Control) and one had a blue valve inserted (Test).

2. Both models were supplied with artificial urine.

3. 30mls of an overnight culture of a clinical strain of *Proteus mirabilis* was pipetted into the drainage tube between the connection with the valve housing and left for 1 hour with no urine flow to allow the bacteria to become established.

4. The urine flow was switched on at a rate of 1ml/min and the models allowed to run until *Pr. mirabilis* was detected in the glass bladder. This was done by removing 5ml of urine from the bladder every 24hrs. pH and viable bacterial numbers were recorded.

5. The time for *Pr. mirabilis* to migrate to the bladder was recorded for the Control and Test models.

6. These experiments were repeated in triplicate.

The study has demonstrated that the valve reliably opened and closed periodically for up to 14 days and prevented the migration of *Pr. mirabilis* up through the drainage system to the bladder when compared to a non-valved continuous drainage model. *Pr. mirabilis* was not detected in any of the valved models (Table 1.).

Table 1 - Summary of times taken for Pr. mirabilis to migrate up to the bladder in Control
and Test Models.

Run 1		Run 2		Run 3	
Control	Test	Control	Test	Control Test	
>120 h	>120 h	144 h	>288 h	168 h	>336 h

## 4. CLINICAL INVESTIGATION OBJECTIVES

The next stage is for the prototype valve to be tested clinically in humans under research conditions; this will establish if the device reliably opens and closes and is safe to use.

#### 4.1 Research Questions:

- 1. Does the valve function reliably and effectively?
- 2. Does the valve provide a safe method of emptying the bladder?

3. Does the valve provide a method of emptying the bladder which is acceptable to users e.g. for comfort?

4. Is a community-based trial of the valve feasible and desirable?

#### 4.2 Objectives

To assess preliminary safety, effectiveness, reliability, comfort and user acceptability of the valve with adults who have a long-term IDC and the feasibility of undertaking future community-based evaluation.

To do this we will:

- determine if the valve functions reliably i.e. automatically opens to drain urine within acceptable individual bladder volumes with a range of patients;
- determine if the valve functions effectively i.e. allows for the complete bladder emptying (< 100ml post void residual) during rest and daily activities;
- determine if the process of filling and automatic draining is comfortable and acceptable for participants;
- collect preliminary data on the potential for bioburden/biofilm following in human use of the valve;
- assess the feasibility of undertaking a future randomised control trial of the valve.

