#### 4.3 Outcomes

4.3.1 Primary outcomes:

Safety: Reliability

• Valve opening - Proportion of observations of automatic valve opening before bladder capacity (500ml or less) is reached - as measured by bladder scanner (Valve Log)

Safety: Effectiveness

- Bladder emptying proportion of valve voids with residual urine <100ml as measured by bladder scanner (Valve Log)
- Participant report (Valve self-report questionnaire) *Comfort*
- Participant report (Valve self-report questionnaire)

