## 5. CLINICAL INVESTIGATION DESIGN

This study a 'first in human' assessment of reliability, effectiveness, comfort and user acceptability with 16 long-term catheter users.

This study will be in one phase over 6 months, and compromise of 2 groups:

Group 1 (n=8)	Safety cohort (n=4)	Interim Safety review	(n=4)	
Group 2 (n=8)				(n=8)

Group 1- The valve will initially be tested in 8 participants who currently use a standard manual valve (without leg-bag). Such participants (and their bladders) will be accustomed to the filling and emptying of the bladder with an IDC in situ and therefore represent the most predictable and safest population on which to test the valve.

This first group will include a safety cohort of participants (n=4). All safety data will be reviewed from the initial 4 participants before further participants can undergo the study investigation. Review of the initial data will include an interim safety report submission to the Medicines and Healthcare products Regulatory Agency (MHRA) in line with the issued Notice of No Objection.

Once all relevant permissions to proceed have been granted, the valve will then be tested in the remainder of standard manual valve participants (n=4) to complete Group 1.

Group 2 - The valve will then be tested with participants (n=8) who currently use a drainage bag with free drainage in order to test the valve with people who are no longer accustomed to the process of filling and emptying the bladder (Group 2).

After use (in both groups), the valves will be examined microbiologically in the University of Southampton laboratory to detect bioburden and/or biofilm to ascertain a baseline for future studies.

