#### Testing Procedure

With the participant sitting (except when transferring to and lying on the bed for bladder scanning):

- 1. Participant puts on pad with pants to secure it in place
- 2. Record participant's self-reported bladder sensations
- 3. Scan bladder and record volume in Valve Log.
- 4. Research nurse fits the lowest pressure valve according to manufacturer's instructions for use and attach a drainage bag for urine collection. Record Valve Batch/Serial Number in Valve Log.
- 5. Record participant's self-reported bladder sensations in valve log
- 6. Scan bladder and record volume in valve log
- 7. If the valve remains open with urine draining freely, replace with the next level pressure valve (up to 3 valves) until free drainage has ceased and the valve remains closed. Record Valve Batch/Serial Number in Valve Log.

URINARY CATHETER 'FILL AND FLUSH' VALVE:

SAFETY, EFFECTIVENESS, ACCEPTABILITY AND FEASIBILITY TRIAL Protocol Version 3.1 20/08/2019 - IRAS: 245818 - ERGO: 41448

- 8. Participant to lie on bed for hourly bladder scanning (record time and volume in Valve Log) until bladder volume is >400mls or the participant experiences bladder discomfort or the valve automatically opens. Record participant's bladder sensations before each scan and:
  - a. If the volume is >400mls or the participant is experiencing discomfort
    - i. Ask the participant to contract abdominal muscles, press down on abdomen or bear down as if trying to pass urine to increase bladder pressure.
    - ii. If the valve opens, proceed as below (b).
    - iii. If the valve does not open, disconnect the valve, attach a new drainage bag and allow the bladder to drain. Stop the trial for that participant.
  - b. If the valve automatically opens:

Southampton

- i. Record the amount of urine voided
- ii. Scan the bladder for any residual volume
- 9. If the valve has opened with a urine volume of less than 500ml, repeat process 7 & 8 at 1 hourly intervals for 5 hours. If the valve did not open before bladder volume reached 500ml, stop testing at this point.

Participants will be requested to drink a minimum of 500mls of fluids over the first two hours, then a minimum of 150mls per hour for the next 3 hours. They will be given a choice of drinks. After testing has ended for that day, participants will be given a new manual valve and/or drainage bag as per usual use.

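### Reliability is defined by each participant's own bladder volume but can only be scored against 500 ml for everyone, and openings after discomfort or prompted straining are left unclassified

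*Protocol*

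**What the plan says.** The objective in Protocol 4.2 sets an individual standard: the valve is reliable if it "automatically opens to drain urine within acceptable individual bladder volumes with a range of patients". The primary outcome in 4.3.1, listed under safety, is the "Proportion of observations of automatic valve opening before bladder capacity (500ml or less) is reached", measured by bladder scanner and taken from the Valve Log.

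On Day 1 (5.6.1), step 9 separates success from failure by a single volume: "If the valve has opened with a urine volume of less than 500ml, repeat process 7 & 8 at 1 hourly intervals for 5 hours", and "If the valve did not open before bladder volume reached 500ml, stop testing at this point". Step 8 asks staff to "Record participant's bladder sensations before each scan", and step 8a begins "If the volume is >400mls or the participant is experiencing discomfort". In that event the participant is asked to strain or bear down. If the valve then opens, step 8a.ii passes the event to branch (b), the branch for automatic opening. If it does not open, the valve is disconnected and that participant's trial stops. Day 2 (5.6.2) repeats this in step 19a.

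Section 5.9.1 plans the range and mean of bladder volume at valve opening for each activity, and frequencies of questionnaire answers.

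**The concern.** The objective asks whether the valve opens in time for the bladder it is attached to. The outcome asks whether it opens before a volume that, in practice, is the same for all participants. Where a participant's acceptable volume is below 500 ml, the two can disagree. The disagreement goes one way: an opening too late for that person still satisfies the outcome.

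The second problem is the word automatic. An opening produced by asking an uncomfortable participant to bear down is not evidence that the valve opens by itself as the bladder fills, yet the procedure files it with those that do.

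At stake is the headline reliability figure of a first-in-human safety study. Section 3.2 also makes it an aim to learn which pressure variant works and in which circumstances. A variant that tends to open only after discomfort or straining could look as reliable as one that opens unprompted.

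**Working it through.** The protocol gives no figure to reproduce, so the check sets its sections side by side.

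1. **Is the limit in 4.3.1 individual or common?** The wording "before bladder capacity (500ml or less) is reached" allows two readings: each person's own capacity with 500 ml as a ceiling, or 500 ml for all.

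2. **Can the individual reading be applied?** It needs a capacity or acceptable volume for each participant, fixed before testing. The pre-testing lists in 5.6.1 and 5.6.2 cover consent, a drink, vital signs and quality-of-life tools, plus demographics on Day 1. The testing steps add bladder sensations and scan volumes. None establishes an individual limit, so this reading cannot be scored.

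3. **Which limit remains?** Step 9 uses 500 ml for every Day 1 participant. Section 5.6.2 has no counterpart to step 9, so for Day 2 the only opening limit is the figure in 4.3.1. The limit is in effect common.

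4. **Opening after recorded discomfort, without straining.** If the volume is within 500 ml, it meets the only volume criterion. Neither 4.3.1 nor 5.9.1 says that it should be treated differently.

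5. **Opening after prompted straining.** Steps 8a.i and 19a.i prompt the manoeuvre, and 8a.ii and 19a.ii route a resulting opening to branch (b). On Day 1, step 9 then continues testing if the volume was below 500 ml. The outcome's word automatic could exclude such an opening, but the routing points the other way and nothing settles it.

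6. **Do other outcomes fill the gap?** Comfort is a primary outcome by questionnaire, but 5.6.2 has the Valve Questionnaire completed after all testing, so it cannot show which opening followed discomfort. The clinical analyses listed in 5.9.1 do not include the logged sensations. Section 6.1.1 records bladder discomfort but does not report it as an adverse event, because it is a study outcome.

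**Illustration only.** The protocol gives no individual volumes. If an acceptable volume were 200, 300 or 400 ml, the band accepted by the outcome but outside the objective would be 500 − 200 = 300 ml, 500 − 300 = 200 ml or 500 − 400 = 100 ml. At 500 ml the band is zero and the definitions agree. These are widths in millilitres. They do not say how many openings would change class.

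**The case against.** The best defence is that 4.3.1 names bladder capacity and adds a ceiling, which fits the individual objective. As a reading of the words this stands: a reader might infer that the outcome plainly sets one fixed limit, and it does not. The limit becomes common only because no individual value is recorded.

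Second, a reader might infer that the protocol scores an opening after discomfort as a success. It has no scoring rule for that case. Because discomfort triggers a prompt to strain, an unprompted opening after recorded discomfort is also a narrow case. This stands too, and it makes the routing of strained openings the more practical part of the problem.

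Third, discomfort is not ignored. It triggers step 8a, it stops the participant's trial if the valve then stays shut, and comfort has its own objective and primary outcome. Keeping mechanical reliability apart from comfort is a legitimate choice. The answer is to report the classes separately, without merging the two outcomes.

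Finally, a reader might infer that Group 2 is hit hardest, since 5 describes it as "people who are no longer accustomed to the process of filling and emptying the bladder". That phrase says nothing about capacity. The remark on reduced capacity in 3.1 concerns manual valves, which are Group 1's usual device. The protocol supports no ranking of the groups.

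**Conclusion.** The concern holds as a mismatch between objective and outcome, together with an unstated classification. The individual standard in 4.2 cannot be applied with the data the protocol collects. The 500 ml limit is the only usable one, and openings after discomfort or prompted straining have no stated place in a primary safety outcome.

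Any resulting error raises the reliability proportion and can arise in either group of 8. Its size cannot be computed: it depends on individual acceptable volumes and on how often openings follow discomfort or straining, and the protocol gives neither. If every participant's acceptable volume were 500 ml or more and no opening followed straining, the proportion within 500 ml would not be inflated. The conclusion assumes that no individual limit is recorded in a form not described in the protocol.

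**What to change.** Reconcile 4.2, 4.3.1, 5.6.1 and 5.6.2 before scoring begins, and state in 4.3.1 that the volume limit is applied in common to all participants. Then classify each opening from the Valve Log as:

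- (i) automatic, with no discomfort recorded earlier in that filling period;
- (ii) automatic, after recorded discomfort;
- (iii) after the straining prompted under step 8a.i or 19a.i.

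Do not count (iii) as automatic. Report (i) and (ii) separately, by group and by valve variant. Make clear that (iii) means the prompted manoeuvre and not the standing, walking and coughing scheduled on Day 2. The separate reporting of (i) and (ii) keeps the individual element of the objective visible, using sensations that are already recorded.

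The cost is a few sentences in 4.3.1 and a mark in the Valve Log for openings that follow straining. The headline reliability proportion may be lower. No volume threshold, care step or visit changes.

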#### 4.3 Outcomes

4.3.1 Primary outcomes:

Safety: Reliability

• Valve opening - Proportion of observations of automatic valve opening before bladder capacity (500ml or less) is reached - as measured by bladder scanner (Valve Log)

Safety: Effectiveness

- Bladder emptying proportion of valve voids with residual urine <100ml as measured by bladder scanner (Valve Log)
- Participant report (Valve self-report questionnaire) *Comfort*
- Participant report (Valve self-report questionnaire)

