#### Testing Procedure

With the participant sitting (except when transferring to and lying on the bed for bladder scanning):

- 10. Participant puts on pad with pants to secure it in place
- 11. Record participant's self-reported bladder sensations
- 12. Scan bladder and record volume in Valve Log
- **13**. Participant fits the lowest pressure valve according to manufacturer's instructions for use and attach a drainage bag for urine collection.
- 14. Record Valve Batch/Serial Number in Valve Log.
- 15. Record participant's self-reported bladder sensations in valve log
- 16. Scan bladder and record volume in valve log
- 17. If the valve remains open with urine draining freely, replace with the next level pressure valve (up to 3 valves) until free drainage has ceased and the valve remains closed. Record Valve Batch/Serial Number in Valve Log.
- 18. Participant will be asked to stand, walk around and cough at specific intervals as per flowchart in appendix C.

URINARY CATHETER 'FILL AND FLUSH' VALVE:

SAFETY, EFFECTIVENESS, ACCEPTABILITY AND FEASIBILITY TRIAL Protocol Version 3.1 20/08/2019 - IRAS: 245818 - ERGO: 41448

- 19. Record participant's bladder sensations before each scan and:
  - a. If the volume is >400mls or the participant is experiencing discomfort
    - i. Ask the participant to contract abdominal muscles, press down on abdomen or bear down as if trying to pass urine to increase bladder pressure.
    - ii. If the valve opens, proceed as below (b).
    - iii. If the valve does not open, disconnect the valve, attach a new drainage bag and allow the bladder to drain. Stop the trial for that participant.
  - b. If the valve automatically opens:
    - i. Record the amount of urine voided
    - ii. Scan the bladder for any residual volume

As with Day 1, participants will be requested to drink a minimum of 500mls of fluids over the first two hours, then a minimum of 150mls per hour for the next 3 hours. They will be given a choice of drinks. After testing has ended for that day, participants will be given a new manual valve and/or drainage bag as per usual use.

If a participant has to stop testing during Day 1 they will not be eligible for any further testing. All data will be collected by an appropriately trained research nurse (RN).

**Valve Questionnaire**: After all testing is completed; participants will complete a Valve Questionnaire to assess the valve for comfort.

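### The primary reliability outcome does not say how to classify openings obtained only by straining, or valves removed before 500 ml, so reliability may be overstated

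*Protocol*

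**What the plan says.** **Outcome and objective.** Section 4.3.1 gives the primary reliability outcome as "Proportion of observations of automatic valve opening before bladder capacity (500ml or less) is reached - as measured by bladder scanner (Valve Log". The matching objective in section 4.2 is a valve that "automatically opens to drain urine within acceptable individual bladder volumes with a range of patients".

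**Day 1 (section 5.6.1, steps 8 and 9).** The bladder is scanned hourly. The trigger for action is: "If the volume is >400mls or the participant is experiencing discomfort". The instruction is then: "Ask the participant to contract abdominal muscles, press down on abdomen or bear down as if trying to pass urine to increase bladder pressure". Two results are possible:

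- The valve opens, step 8a(ii): "If the valve opens, proceed as below (b", with the bracket closing after the letter. Branch (b) is the one for a valve that opens automatically. It records the volume voided and the residual.
- The valve stays shut, step 8a(iii): "If the valve does not open, disconnect the valve, attach a new drainage bag and allow the bladder to drain". The trial ends for that participant.

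Step 9 continues testing for up to 5 hours after an opening below 500 ml. Otherwise: "If the valve did not open before bladder volume reached 500ml, stop testing at this point".

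**Day 2 (section 5.6.2, step 19).** The trigger, the manoeuvre and both branches are repeated, but nothing corresponds to step 9. A participant stopped on Day 1 is not tested again.

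**Analysis and safety recording.** Section 5.9.1 is descriptive and summarises bladder volume at each opening, by activity. Section 6.1.1 lists a valve that does not open as a solicited adverse event, recorded but not reported. No target value is set for the reliability proportion.

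**The concern.** The outcome is about automatic opening, but the procedure puts two kinds of opening through one branch: those that occur unaided and those that occur only after the participant raises bladder pressure on request. If the record does not tell them apart, no later analysis can.

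The volumes also differ. Removal is triggered above 400 ml, or at any volume with discomfort, while step 9 and the outcome use 500 ml. A valve removed shut between 401 and 499 ml, or earlier for discomfort, is not said to be a failure, a censored observation or an exclusion.

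This is a primary safety outcome for a device used in humans for the first time. An overstated figure would carry into the decision on a community-based trial.

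**Working it through.** The protocol states no figure for this outcome and no sample-size calculation, so there is nothing to reproduce. Two checks apply.

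**1. Can a shut valve still be seen at 500 ml or more on Day 1?**

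Inputs from section 5.6.1: hourly scans, action above 400 ml, and minimum intake of 500 ml over two hours (250 ml/h) followed by 150 ml/h. Assumptions: steady filling at r ml/h, no earlier discomfort, and a first scan above 400 ml that is uniform on (400, 400 + r).

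P(that scan is already at 500 ml or more) = max(0, 1 − 100/r)

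| r (ml/h) | Probability |
|---|---|
| 100 or less | 0 |
| 150 | 1 − 100/150 = 0.33 |
| 200 | 1 − 100/200 = 0.50 |
| 250 | 1 − 100/250 = 0.60 |

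Hourly volumes from an empty bladder at the minimum intake, with output as an assumed share of intake:

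- 100%: 250, 500 ml. The first scan above 400 ml is at 500 ml.
- 80%: 200, 400, 520 ml. It is at 520 ml.
- 60%: 150, 300, 390, 480 ml. It is at 480 ml, and a shut valve is removed there.

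So the 500 ml failure can be reached, but many shut valves would be removed below it. Earlier discomfort would make such removals more common.

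**2. How far can the classification move the result?**

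Assumed illustration with 16 participants: 8 valves open unaided, 4 only on straining, 4 never.

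*One observation per participant, non-openings kept as failures:*

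- Unaided openings only: 8/16 = 50% (exact 95% CI 24.7% to 75.3%).
- Strained openings also counted, all below 500 ml: (8 + 4)/16 = 75%.
- If a share w of the strained openings occurs at 500 ml or more and so fails the limit, the proportion is 0.50 + 0.25 × (1 − w). This is 0.67 at w = 1/3 and 0.60 at w = 0.6.

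*Repeated observations:* a valve that opens is retested, and one that fails on Day 1 is stopped. Assume k openings per day over two days for each of the 12 opening valves, all below 500 ml, and one failed observation for each of the other four. The proportion is 24k/(24k + 4).

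| k | Strained openings counted | Unaided only, 16k/(24k + 4) |
|---|---|---|
| 1 | 24/28 = 86% | 16/28 = 57% |
| 2 | 48/52 = 92% | 32/52 = 62% |
| 3 | 72/76 = 95% | 48/76 = 63% |

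Pooling observations therefore raises even the unaided figure above the per-participant 50%. The strained openings add the rest.

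**The case against.** The strongest reply is that branch (b) only lists what staff do after any opening: measure the void and scan the residual. It does not say that a strained opening enters the numerator in section 4.3.1, and the word automatic there could exclude it. The valve is designed to respond to rising bladder pressure, so an opening under abdominal pressure without manual operation is arguably automatic. Denominator rules are commonly left to an analysis plan, which is not shown. An action trigger below an outcome limit is not in itself a contradiction: step 8a(iii) can be read as covering valves that never open, and step 9 as covering those that open late. The Valve Log and the flowcharts in Appendices B and C are also not shown.

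Much of this stands. It means that overstatement is possible, not certain. It does not remove the gap. The text has no visible flag for strained openings, no stated class for a valve removed shut, and no Day 2 rule matching step 9. An analysis plan cannot recover a distinction that was not recorded.

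A reader might go further and infer that the outcome can hardly be failed, or will be near 100% whatever the valve does. The documents do not support that. A valve disconnected unopened is naturally a failed observation. Hourly scans can first find 500 ml or more. Non-opening is recorded as a solicited event. A forced 100% needs both that disconnected valves leave the denominator and that no scan reaches 500 ml. Since no success threshold is set, only single observations can fail.

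A reader might also infer that this coding decides who has completed under the stopping rule in section 6.3. That section does not tie completion to the outcome, and a participant whose valve never opens is stopped.

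**Conclusion.** The point holds as a gap in classification with a possible upward bias. Openings obtained only by straining share a branch with automatic ones, and valves that stay shut are removed on a rule that does not match the 500 ml in step 9 and the outcome.

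In the illustration the reported figure moves from 50% to as much as 75% per participant. Pooling repeated openings takes it to 86% to 95%. These sizes rest on the assumed 8/4/4 split, on strained openings below 500 ml, and on the assumed number of openings per day. If strained openings often occur at 500 ml or more, the per-participant figure falls to 60% to 67%. If the Valve Log already separates these openings, what remains is to state the numerator and denominator and reconcile the volumes.

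**What to change.** In section 4.3.1 and the Valve Log, code each fill started with a closed valve as one of:

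- (i) opened without straining;
- (ii) opened only after the manoeuvre in step 8a(i) or 19a(i);
- (iii) not opened and valve disconnected, with the last volume and the reason;
- (iv) unfinished when the session ended.

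The main reliability proportion is the number in (i) with volume within the outcome limit, divided by (i) + (ii) + (iii). Report (ii) separately. Report (iv) but leave it out of the denominator: if it counted as failure, a faultless valve with two openings and one unfinished fill would score 2/3. Add a per-participant summary, because valves that open contribute more observations than valves that fail.

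Sections 4.3.1, 5.6.1 and 5.6.2 must be reconciled on the volume that ends a test, including whether Day 2 needs a counterpart to step 9. This review does not say which volume is right.

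The cost is some wording and one more Valve Log field. The reliability figure may be less favourable. The field has to be in place before data collection, because the distinction may not be recoverable afterwards.

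### Opening is counted per observation although a participant stops at the first non-opening, so reliability reads too high if participants differ; the emptying figure is conditional on the valve opening

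*Protocol*

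**What the plan says.** Section 4.3.1 defines two device-measured primary outcomes, and neither has the participant as its unit. Reliability is the "Proportion of observations of automatic valve opening before bladder capacity (500ml or less) is reached". Effectiveness is the "proportion of valve voids with residual urine <100ml as measured by bladder scanner". Section 5.9.1 plans descriptive statistics, with volumes summarised per valve opening and activity, and defines no participant-level proportion.

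Section 5.6 determines how many observations each person gives:

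- On Day 1 (step 8a) and Day 2 (step 19a), if the volume is above 400 ml or there is discomfort, and the valve does not open even with straining, the instruction is "Stop the trial for that participant".
- Day 1 step 9 adds: "If the valve did not open before bladder volume reached 500ml, stop testing at this point".
- If the valve opens below 500 ml, the nurse is to "repeat process 7 & 8 at 1 hourly intervals for 5 hours".
- After an opening the step is "Scan the bladder for any residual volume". No result of that scan stops testing.
- At the end of section 5.6.2: "If a participant has to stop testing during Day 1 they will not be eligible for any further testing".

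The participant-reported part of the primary outcomes, including comfort, comes from the Valve Questionnaire, described at the end of the Day 2 section: "After all testing is completed; participants will complete a Valve Questionnaire to assess the valve for comfort".

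**The concern.** The number of reliability observations that a participant contributes depends on the outcome being measured. A valve that works is observed again and again over two days; one that fails at once is observed once and then leaves. A proportion taken over all observations gives most weight to the participants in whom the valve works.

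Emptying is affected differently. A residual of 100 ml or more stops nobody, so stopping at failure is not the mechanism. Instead, a valve that never opens produces no void, and that participant is absent from the denominator. The figure answers how well the bladder empties when the valve opens, not how many users the valve empties well.

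Section 4.2 asks whether the valve opens reliably across a range of patients, which is a question about people. Section 4.1 asks whether a community trial is feasible and desirable, and a reliability figure that leans upward would feed into that answer.

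**Working it through.** **Inputs from the protocol.** 16 participants in two groups of 8 (section 5). Hourly repeats for 5 hours on Day 1; taking Day 2 as similar, at most about 5 per day and 10 over two days. Stop at the first non-opening. The sample size of 16 is given without a calculation (section 5.3), so there is no planned figure to reproduce.

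**Assumptions, because the protocol gives no value.** Each completing participant yields m = 4, 6 or 10 fills. A stop for non-opening scores as one failed observation. The mean chance of opening is 70%.

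**Formula.** For a participant with opening chance p, stopped at the first failure, with at most m observations:

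- expected observations E[T] = 1 + p + … + p^(m−1)
- expected openings E[S] = p + p² + … + p^m = p × E[T]

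**Step 1: all participants share one p.** E[S]/E[T] = p exactly, so there is no upward bias. With only 16 people the simulated mean is slightly low: about 69% for p = 0.70, and 73.9% to 74.3% for p = 0.75.

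**Step 2: p differs between participants.** Let p follow Beta(a, b), so that E[p^k] is the product of (a+i)/(a+b+i) for i = 0 to k−1. The intraclass correlation is 1/(a+b+1). Example, Beta(0.7, 0.3) with m = 4: E[p], E[p²], E[p³], E[p⁴] = 0.700, 0.595, 0.5355, 0.4953. Then E[T] = 1 + 0.700 + 0.595 + 0.5355 = 2.8305, E[S] = 0.700 + 0.595 + 0.5355 + 0.4953 = 2.3258, and the ratio is 0.822. Simulated trials of 16 participants average 0.814.

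Simulated mean per-observation proportion, 16 participants, true mean 70%:

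| Spread between participants | m = 4 | m = 6 | m = 10 |
|---|---|---|---|
| None | 69% | 69% | 69% |
| Mild: Beta(7, 3), correlation 1/11 = 0.09 | 72% | 73% | 74% |
| Moderate: Beta(2.1, 0.9), correlation 1/4 = 0.25 | 76% | 78% | 81% |
| Extreme: Beta(0.7, 0.3), correlation 1/2 = 0.50 | 81% | 84% | 88% |

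**Step 3: a case that can be done by hand.** Suppose 12 of 16 valves always open and 4 fail at the first observation. The per-observation proportion is 12m/(12m + 4): 48/52 = 92%, 72/76 = 95%, 120/124 = 97%. The participant proportion, here also the mean chance of opening, is 12/16 = 75% (exact Clopper–Pearson 95% CI 48% to 93%).

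**Step 4: emptying.** Suppose 4 of 16 never open and 90% of the others' voids leave under 100 ml. The per-void figure is 90%. Averaged over all 16, with the 4 as failures, it is (12 × 0.90 + 4 × 0)/16 = 10.8/16 = 67.5%. With 2 or 8 non-openers it is 14/16 × 0.90 = 78.8% or 8/16 × 0.90 = 45%, while the per-void figure stays at 90%.

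**The case against.** The upward bias is not automatic. Step 1 shows none if every participant has the same chance of opening, and the protocol does not quantify how much participants differ. This stands, and the point is stated as conditional. Differences are nevertheless likely on the protocol's own account: section 3.2 says that bladders work at different pressures, and section 5 deliberately recruits users accustomed and unaccustomed to bladder filling.

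The analysis is descriptive, with no interval, test or target for these proportions. A reader might infer that the plan claims false precision by treating repeated fills as independent. It does not: no interval is planned. Listings per participant could also appear in a SAP. But the outcome definitions and the stopping steps are fixed in the protocol, and together they produce the problem.

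A reader might also set the per-observation figure under extreme spread with 6 fills (84%) against the 44% of participants with no failure in the same simulation, and call the gap bias. Those are different quantities. With a common chance of 0.70 and no upward bias, only 0.7⁶ = 12% of participants would get through six fills without a failure. The bias in that scenario is 84% against 70%.

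On the questionnaire, a reader might infer that anyone stopped on Day 1 is left out. The text does not say so: for a stopped participant, testing is complete at the stop, and section 5.9.1 summarises each occasion of completion. The flow charts in Appendices B and C are not in the text available, so timing cannot be checked there. Bladder sensations are recorded before each scan, and discomfort and non-opening are recorded as solicited events (section 6.1.1), so early failures are not lost. What remains is an ambiguity worth closing.

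**Conclusion.** The point holds in a limited form. For reliability, the observation-level denominator combined with stopping at the first non-opening overstates the mean chance of opening whenever that chance varies between participants. With a 70% mean and 4 to 10 fills, the excess is about 2 to 4 percentage points under mild spread and 11 to 18 under extreme spread; it is absent with no spread. The mean, the spread and the fill counts are assumptions, so the direction is likely but the size cannot be derived from the protocol.

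For emptying, the figure is conditional on opening, and the gap depends on how many valves never open. The stronger reading, that stopping at failure biases the emptying proportion in the same way, is not supported, because a high residual does not end testing.

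This does not undermine a descriptive first-in-human study; the trial-level completion rule in section 6.3 already counts participants. It should be corrected because the primary figures as defined can mislead and the remedy is cheap.

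**What to change.** **Sections 4.3.1 and 5.9.1.** Keep the per-observation and per-void proportions. Beside each, report a participant-level proportion out of all participants fitted with a valve:

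- Report opening and emptying separately, since section 4.2 keeps them apart. Fix in advance what counts as success for a participant in each (for example, every observation or void, or a stated share), so that one marginal residual is not left to later judgement.
- Report by day and by group, with an exact 95% CI.
- Show the number of observations per participant, because someone with more fills has more chances to fail.
- Count Day 1 stops for non-opening as failures in the overall and Day 2 denominators, and state that such a stop scores as a failed observation.
- Label the per-void emptying figure as conditional on opening.

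**Section 5.6.2.** State that anyone stopped early also completes the Valve Questionnaire, at the time of stopping. Settle this before enrolment, since responses missed then may not be recoverable.

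**Cost.** Wording in three sections and an earlier questionnaire for some participants. No extra visits or participants are needed, and the stopping steps are untouched. The price is wide intervals and a less favourable headline figure: in the example in step 3, 75% (48% to 93%) would stand beside 92–97%.
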